This survey protocol describes the background and implementation design for the coverage survey that will be conducted in Malawi during October 2017. Mapping was conducted in January to March 2012 by the Ministry of Health (MoH) which has informed the strategy for the implementation of the preventive chemotherapy (PC) programme for schistosomiasis (SCH) and soil transmitted helminth infections (STH). The aim of this coverage survey is to evaluate the effectiveness of the PC campaign in July 2017 in reaching the target population.

Background to the Coverage Survey

Schistosomiasis or Bilharzia is a parasitic disease caused by infection with the trematode blood-flukes schistosomes. In sub-Saharan Africa, two major forms of human schistosomiasis occur: intestinal schistosomiasis caused by mainly *Schistosoma mansoni* infection and urinary schistosomiasis due to *Schistosoma haematobium* infection. Soil-transmitted helminthiasis is caused by infection with a group of intestinal nematode worms, most important of which within much of sub-Saharan Africa are the hookworms (both *Ancylostoma duodenale* and *Necator americanus*), the roundworm (*Ascaris lumbricoides*) and whipworm (*Trichuris trichiura*). Both schistosomiasis and STH are among the neglected tropical diseases (NTDs), which remain serious public health problems, posing unacceptable threats to human health and welfare.

The World Health Assembly resolution 54.19 urges all member states to regularly treat at least 75% of all school aged children who are at risk of morbidity from schistosomiasis and STH with Praziquantel (PZQ) and Albendazole or Mebendazole (ALB or MBD), respectively. To determine if these global goals are being reached, each national programme *routinely reports* drug coverage. This metric is calculated using the number of treatments distributed during a round of PC recorded in treatment registers and/or tally sheets for the numerator, and population figures (often obtained from routine census figures) as the denominator.

In order to monitor and support NTD programme performance, independent drug *coverage surveys* are recommended by the WHO (WHO 2006). These coverage surveys should be carried out across all areas given PC, particularly at crucial time points during the programmes i.e. in the first year of the programme, in cases where coverage might be suspiciously high or low, to ensure any corrective actions where needed. In areas where routinely reported coverage is low, additional methods i.e. Key Informant Interviews and Focus Group Discussion are recommended to assess the causes of low coverage (WHO, 2005; WHO, 2010).

SCI currently uses cluster-sample surveys similar to those widely used by the Expanded Programme in Immunisation (EPI) and in other NTD programmes (WHO 1991; WHO 2005; Worrell and Mathieu 2012; Cromwell *et. al.* 2013; Baker *et. al.* 2013). The accuracy of routinely reported coverage estimates can be assessed by comparing these with survey-derived coverage estimates and their 95% confidence intervals. In addition to identifying over and under-reporting, in routinely collected data, these coverage surveys also provide data to assess other issues such as, MDA delivery strategies, biases in treatment coverage for example by gender, school enrolment, and examination of possible reasons for coverage failure. This information assists in the identification for recommended actions to improve programme delivery.

Schistosomiasis and STH in Malawi

Intestinal and urogenital schistosomiasis caused by infection with *S. mansoni* and *S. haematobium* is a widespread public health problem in Malawi. The Malawian Ministry of Health (MoH) has an ongoing national scale treatment programme for schistosomiasis control. All 29 districts are at varying stages of programme implementation. All districts are endemic for *Schistosoma mansoni* and *S. haematobium* and have received five or more rounds of annual treatment with praziquantel (PZQ) and albendazole (ALB) for Soil Transmitted Helminths (STH) since 2009 (MoH report). The mean prevalence of *S. mansoni* has reduced from 2.23% eggs per gram (epg) at baseline to 0.82% epg at the third follow up. With the prevalence of heavy infection reducing from 0.19% to 0. The prevalence of *S. haematobium* has also reduced from 9.21% at baseline to 3.64% at follow up three. Prevalence of heavy infection has reduced from 1.60% at baseline to 0.73% at baseline and mean intensity of infection (eggs/10ml) has reduced from 3.59 to 1.12.

Previous mapping

Prior to SCI working with the MoH in 2011 baseline mapping surveys had been conducted in a number of the districts between 2003 and 2010 to enable the national program to commence mass treatment campaigns. The first mapping exercise was carried out in Malawi in 2003 to determine the distribution of infection and help guide planned control through treatment. The surveys that were conducted focused on urine filtration to detect S. *haematobium* and found there was a significant burden of disease in all targeted districts. Results indicated both a widespread occurrence of infection, and a marked variability in infection prevalence. However, information relating to *S. mansoni* and STH infection was not gathered. Since the baseline mapping in 2003, 26 out of 28 districts have been mapped. Mapping results presented between 2003 and 2010 have varying protocols and results are taken straight from MoH unpublished reports¹.

Treatment History

Due to the willingness of the MoH, financial support from SCI and availability of purchased and donated PZQ and ALB, Malawi has conducted national treatment annually since 2012. This followed limited treatments which were distributed between 2009 - 2012 in several parts of the country.

All districts in Malawi have now received at least five rounds of treatment. From 2012 to date the target population within each district has expanded from targeting school-age children (SAC) through school treatments, to treating SAC through school and communities and some adults, to now conducting both school and community treatments targeting all SAC as well as adults in known high risk areas (which may sometimes be whole districts) based on previous mapping results. In 2014 districts were asked to begin categorising health centres, schools and villages into areas of high risk or not. This was based on either previous mapping results, abundance of water bodies or high risk agricultural activities i.e rice farming or fishing. Categorisation of high risk areas is based on local knowledge and practices of the areas and population.

¹ S:\SCI - post 3 June 2011\Current programmes\DFID\ICOSA\COUNTRIES\Malawi\Mapping\pre-ICOSA mapping\ Baseline Prevalence studies from [name]

Category	Prevalence	Action	
High-risk	≥50%	Treat all school-age children once a year	Simultaneously treat all adults once a year
Moderate-risk	≥10% but <50%	Treat all school-age children once a year	Also treat adults considered to be at risk
Low-risk	<10%	Treat all school-age children twice during their primary schooling	Praziquantel should be available in dispensaries and clinics

Table 1: WHO guidelines for treatment of schistosomiasis (WHO 1993, 1998)

Previous Coverage Surveys

Malawi has conducted three coverage surveys the first in 2012, second in 2014 and third in 2016.

2012

The first coverage survey in 2012 was conducted in two districts Mangochi and Mulanje. In SAC, overall therapeutic coverage rate in the survey was 75.6% (95% CI: 68.5%, 82.7%) for PZQ, and lower at 55.7% for ALB (95% CI: 48.2%, 63.2%). There were significant differences in coverage by district, with coverage for both drugs higher in Mulanje than Mangochi. Gender differences in coverage were minimal in both districts. Nevertheless, there was a very large effect of school attendance, with children attending school approximately 4-6 times more likely to receive both PZQ and ALB, in both districts. Reported school attendance rates were high among SAC (91% overall, 87% in Mangochi and 95% in Mulanje; such that school-attending children drove the overall coverage patterns

2014

In 2014 treatment was delivered in all 28 districts. All districts were told to target adults in hot spot areas within their districts as well as carrying out community treatment to capture non-attending children. The coverage survey was carried out in August 2014, during school holidays. Six districts were purposively selected for a KAP survey pre-MDA and it was decided these districts and villages would be revisited post MDA to carry out a post-MDA KAP and coverage survey. Six districts Dedza, Salima, Rumphi, Nkhata Bay, Blantyre and Chikwawa were chosen as areas to examine in greater detail their reported versus actual coverage.

This survey took place over four weeks in August 2014, within 3 months of MDA being implemented, and 2100 adults, 1492 attending children and 204 non-attending SAC were interviewed throughout the six districts.

Findings from this survey show that all but one district managed to reach the 75% coverage target for SAC (Figure 2). This is reflected in the reported coverage received by the districts and Chikwawa was known to have particularly low coverage during the MDA. They were asked to carry out an extensive mop up. Although and improvement from the 2012 survey results, the 2014 coverage survey reported that non-attending SAC coverage was still under 40% for the surveyed districts.

Figure 2: Results from previous coverage survey in 2014. Chikwawa, Rumphi and Salima were selected to be revisited during the 2016 coverage survey.

2016

The 2016 coverage survey was conducted in six districts. One district in each region was purposively selected (Chikwawa, Rumphi and Salima), as these were previously surveyed during the 2014 coverage survey and results had demonstrated a need for improvement. In addition, three other districts randomly selected, one from each of the same three region were also surveyed Mchinji, Karonga and Neno districts.

Overall, the surveyed coverage was above the WHO recommended coverage of 75% of SAC in 5 of 6 districts surveyed. When adjusting for population size Mchinji fell below the 75% coverage for SAC. Reported coverage was not significantly different from surveyed coverage in four of the districts for ALB and PZQ, reported coverage was significantly different than surveyed coverage in the remaining two remaining districts, one higher and one lower than reported.

This survey also found there was a significant difference in the coverage between those who do and do not attend school for all districts and there was no significant difference in coverage between the genders. The full protocol and recommendations report can be found here:

https://share.imperial.ac.uk/fom/IDE/SCI/The%20Hub/MWI_2016CoverageSurveyProtocol_EN.docx

https://share.imperial.ac.uk/fom/IDE/SCI/The%20Hub/MWI_Coverage_Recommendations_Report_ EN.docx

Details of the MDA in Malawi 2017

The MDA took place between the 10-14th July 2017. The MDA was conducted in every district in Malawi except the islands of Likoma. SAC were targeted in every district and treatment predominantly delivered in schools for the SAC, as well community-based treatments for children who do not attend school and adults in the high-risk areas.

In addition to the standard radio campaigns and social mobilisation that are conducted annually, the MoH was supported by SCI and Development Media International (DMI) with the delivery of an enhanced media plan which involved 3×1 minute radio clips which started with the Doctor testimonial (25/6/17 - 1/7/17), followed by the Mother testimonial (2/7/17 - 8/7/17) and lastly the clip "Give me my breakfast" Appendix F. Each of the clips was broadcast 70 times (7 times adjacent to the News), across 9 radio stations and in 4 languages: Chichewa, Lhomwe, Tumbuka and Yao.

Coverage targets for MDA in 2017

The aim of the MDA was to target school aged children (SAC) and adults as follows:

	Praziquantel (PZQ)	Benzimidazoles (ALB)
Pre-SAC	Not targeted	Not targeted
SAC attending school	> 75%	> 75%
SAC not attending school	> 75%	> 75%
At-risk adults	> 75%	> 75%

With the following definitions:

- Pre-SAC: 1 to 4 years
- SAC: 5 to 14 years
- Child attending primary school: which is defined as 'attendance at some point during the school year'. This based on the parents' or guardians' report as to whether the child is currently at school or, if not, whether the child attended school at some time during the school year. If the answer to either question is "yes", the child is considered to have attended in the reference school year, even if currently absent or out of school.²
- At-risk adults:, typically individuals ≥ 15 years at the implementation/sub-implementation unit

² UNESCO definition Children Out Of School: Measuring Exclusion From Primary Education http://www.uis.unesco.org/Library/Documents/oosc05-en.pdf

Reported coverage from the MDA

Reported coverage from the most recent 2017 MDA is available for all districts except Chitipa at this time.

	REGISTRATION SCHOOL						TREAT	MENT WITH P	RAZIQUANTEL	SCHOOL	
	MALE	FEMALE	MALE	FEMALE		MALE	FEMALE	MALE	FEMALE		
DISTRICT	5-14	4YRS	15	YRS+	TOTAL	5-14	4YRS	15	SYRS+	TOTAL	COVERAGE
Karonga	48,339	48,782	10,367	8,515	116,003	41,580	41,883	8,242	6,875	98,580	85
Rumphi	27,586	27,318	4,784	3,328	63,016	24,258	24,240	3,770	2,850	55,118	87
Chitipa					-					-	-
Dedza	86,956	95,754	17,981	17,013	217,704	81,557	91,239	16,435	15,573	204,804	94
Salima	48,618	52,043	9,038	8,711	118,410	42,128	45,734	7,644	7,375	102,881	87
Mchinji	67,574	75,612	7,843	6,955	157,984	57,192	65,391	6,797	6,139	135,519	86
Ntheu	67,636	73,130	13,486	12,176	166,428	55,025	59,559	10,343	9,442	134,369	81
Country Total	1,870,598	1,788,119	336,811	327,905	4,323,433	1,639,582	1,626,800	288,779	253,669	3,808,830	88

	REGISTRATION SCHOOL						TREAT		ALBENDAZOLE S	SCHOOL	
	MALE	FEMALE	MALE	FEMALE		MALE	FEMALE	MALE	FEMALE		
DISTRICT	5-14	IYRS	15	YRS+	TOTAL	5-14	4YRS	15	SYRS+	TOTAL	COVERAGE
Karonga	48,339	48,782	10,367	8,515	116,003	41,580	41,883	8,242	6,875	98,580	85
Rumphi	27,586	27,318	4,784	3,328	63,016	24,258	24,240	3,770	2,850	55,118	87
Chitipa					-					40,917	#DIV/0!
Dedza	86,956	95,754	17,981	17,013	217,704	55,483	61,791	9,464	9,147	135,885	62
Salima	48,618	52,043	9,038	8,711	118,410	42,128	45,734	7,644	7,375	102,881	87
Mchinji	67,574	75,612	7,843	6,955	157,984	57,192	65,391	6,797	6,139	135,519	86
Ntheu	67,636	73,130	13,486	12,176	166,428	55,025	59,559	10,343	9,442	134,369	81
Country Total	1,870,598	1,788,119	336,811	327,905	4,323,433	1,399,774	1,408,166	256,519	213,128	3,277,587	76

	REGISTRATION COMMUNITY						TREATME	NT WITH PRA	ZIQUANTEL CO	MMUNITY	
	MALE	FEMALE	MALE	FEMALE		MALE	FEMALE	MALE	FEMALE		
DISTRICT	5-14	IYRS	15	YRS+	TOTAL	5-1	4YRS	15	YRS+	TOTAL	COVERAGE
Karonga	3,310	3,537	16,711	18,394	41,952	2,552	2,745	15,260	16,331	36,888	88
Rumphi	2,967	2,928	12,950	13,585	32,430	2,575	2,468	11,594	12,044	28,681	88
Chitipa					4,033					3,509	87
Dedza	44,496	45,678	36,319	44,145	170,638	35,080	38,567	30,420	39,753	143,820	84
Salima	17,817	20,320	36,967	47,262	122,366	13,998	16,264	32,130	41,365	103,757	85
Mchinji	8,364	8,833	9,366	11,165	37,728	7,811	8,224	8,075	9,586	33,696	89
Ntheu	18,267	19,019	22,357	28,664	88,307	15,058	16,275	19,115	25,091	75,539	86
Country Total	524,740	583,686	936,904	1,208,422	3,467,590	522,312	600,837	836,477	1,034,036	2,993,662	86

	REGISTRATION COMMUNITY					TREATM		BENDAZOLE CO	MMUNITY		
	MALE	FEMALE	MALE	FEMALE		MALE	FEMALE	MALE	FEMALE		
DISTRICT	5-14	4YRS	15	YRS+	TOTAL	5-14	4YRS	15	SYRS+	TOTAL	COVERAGE
Karonga	3,310	3,537	16,711	18,394	41,952	2,552	2,745	15,260	16,331	36,888	88
Rumphi	2,967	2,928	12,950	13,585	32,430	2,562	2,447	6,809	6,990	18,808	58
Chitipa					4,033					-	-
Dedza	44,496	45,678	36,319	44,145	170,638	20,586	23,626	12,382	15,980	72,574	43
Salima	17,817	20,320	36,967	47,262	122,366	13,938	16,188	31,448	40,645	102,219	84
Mchinji	8,364	8,833	9,366	11,165	37,728	7,814	8,232	8,076	9,604	33,726	89
Ntheu	18,267	19,019	22,357	28,664	88,307	15,058	16,275	19,115	25,091	75,539	86
Country Total	524,740	583,686	936,904	1,208,422	3,467,590	392,395	436,140	594,041	820,062	2,242,638	65

Study Aim

This survey protocol is designed to monitor the treatment coverage of PC with PZQ and ALB for the MDA campaign in 2017.

Ethical approval

The MoH in Malawi has granted ethical approval and a letter has been sent

https://imperiallondon.sharepoint.com/sites/fom/SCI/The%20Hub/MWI_Ethical%20Approval_Coverage_20 17.docx?d=w0e80b9b922da45bca382cd0e9f66800b&csf=1

Coverage surveys have been granted ethical approval by Imperial College Research Ethics Committee (ref: ICREC_8_2_2).

Study Objectives

The objectives of the coverage survey are:

Survey Objective (SO) 1. To measure validated treatment coverage of PZQ and ALB in SAC, and adults relative to coverage targets

SO 2. To compare reported and validated coverage of PZQ and ALB for SAC and adults

SO 3. To assess coverage in SAC and adults disaggregated by gender

SO 4. To assess coverage in SAC disaggregated by school attendance

SO 5. Collect information on why targeted eligible individuals did not receive or accept treatment

- SO 6. To assess the impact of radio campaigns on improving knowledge about schistosomiasis
- SO 7. To assess whether radio campaigns improved attendance/coverage of treatment with PZQ and ALB

Where validated coverage rate is defined as:

Total number of interviewed individuals that ingested the target drug Total number of interviewed individuals * 100 %

Note that people interviewed but with missing information on whether they ingested the drug will be assumed to have **not** taken the drug for the purposes of calculating validated coverage.

Study Design

Overview

The coverage survey will take place in nine implementation units (IUs) known as the district. Each IU will be considered separately. Within each IU, the survey will be household (HH) based in randomly selected villages. See Appendix D for a detailed explanation of the statistical approach to the coverage survey.

Survey team

Interviewers must not have been involved in any previous activities related to the NTD programme, specifically the MDA, to ensure that they remain unbiased.

Selection of enumerators will be done by the Programme Managers, ensuring that none of the interviewers were involved with the MDA in July 2017. The majority of interviewers have experience in coverage surveys, but everyone will attend compulsory training to ensure standardisation of knowledge and ability to carry out coverage surveys. Training will include teaching about schistosomiasis and soil transmitted helminth infections as well as familiarisation with the health questionnaires and the phones that the information will be stored on.

Although programme managers will not take part in any of the individual interviews in interviewee households, they will facilitate in the training and logistics of the survey as well as support the teams of enumerators if problems arise.

See Appendix A for more details of the survey teams and logistics.

Timing of survey

Coverage surveys should ideally take place as soon as possible following treatment (especially in areas with frequent MDAs) to minimise recall bias³.

The survey should also take place during the day, and preferably not during school holidays⁴.

In Malawi the coverage survey will take place in October, which is 4 months following the MDA. The survey will take place during the day and will not be during the school holidays.

Implementation unit selection

The number of IUs selected for a coverage survey is generally dependent on budget and logistical reasons. Typically, at least 10% of the eligible IUs should be surveyed. See Appendix D for more information on approaches to IU selection.

In Malawi the IU is the district. The coverage survey will take place in 9 IUs. Each implementation unit will be treated independently in the analysis.

Nine districts were originally selected for the survey, three from each region of Malawi: Central, North and South. Between September and October 2017, in the Southern districts of Malawi, health care workers, local leaders and medical services were attacked in villages due superstition surrounding witchcraft. It was decided for the security of survey teams that the Southern districts would not be visited and, therefore, the selection of districts was revisited. The districts originally selected in the Central and North were kept and after discussion with the MoH additional 3 districts were chosen in these regions based on safety and results from the MDA.

Districts were purposively selected for this survey, four of which were surveyed in 2016, based on safety and whether they were surveyed previously. One of the districts (Salima), as well as Dedza districts, were selected based on poor socioeconomic status, risk of schistosomiasis and level of coverage for an additional qualitative

³ Several recent studies demonstrate that recall bias may not affect accurate reporting of treatment in populations receiving integrated MDA (Knipes *et. al.* 2014; Budge *et. al.* 2016)

⁴ Several SCI coverage surveys conducted during school holidays revealed that the same populations of SAC that received treatment were not available during the school holidays.

survey (protocol available on request). Although districts were purposively selected, the villages and traditional areas were randomised during the selection process.

District	Selection Criteria	Part of Qualitative survey
Salima	Surveyed Previously	Yes
Karonga	Surveyed Previously	
Mchinji	Surveyed Previously	
Rumphi	Surveyed Previously	
Ntcheu	Not surveyed previously	
Dedza	Not surveyed previously	Yes
Chitipa	Not surveyed previously	

Number of villages and households to survey within each IU

Sample size calculations indicated that 17 villages per IU, and 15 HHs per village are required to obtain 9% precision on the coverage of SAC and adults within each district. As the MDA was community-wide, two adults will be randomly sampled, and to capture more information about school attendance rates, all eligible children within a HH will be interviewed. See Appendix D for full details of sample size calculations.

Selection of villages to survey within each IU

A list of all traditional areas (TAs), and all their villages, within the selected districts were collected from the district health offices. The list of all TAs and their villages will ensure all villages have the opportunity to be selected. Each village was allocated a number and was then randomly selected by the in-country team using a random number generator until 18 villages per district were selected. The sample size calculation requires 17 villages, for logistical purposes 18 villages have been selected so that each team will visit 6 villages per district.

A short list of 'reserve villages' was provided, such that if a selected village cannot be visited for security or other unpredictable reasons, it can be replaced with another in the same district. See Appendix B: Coverage Survey Interviewer Manual for more details. Appendix E has a list of all selected villages and reserves

Selection of households to survey within each village

HH selection will be performed on site. Selection will be random, with the methodology dependent on whether HHs lists are available (see data collection protocol). If lists are not available HH selection will by the modified random walk procedure (please see data collection protocol).

Although ideally the survey would include nomadic populations and transient communities, because this is a HH-based survey, those without a fixed residence at the site selected for the coverage survey will not be included in the survey target population.

Selection of individuals to survey within each household

The HH or another responsible individual will be interviewed to obtain the HH information. Two adults within each HH will be randomly selected for individual interview as well as all the children in that household. See Appendix C for more details of individual interview procedures.

Study Participant Recruitment

Consent: The village chief will be notified about the study at least a week prior to the survey by the team leader, survey coordinator, or through other channels. Upon arrival in the village, there will be a meeting with

the village chief where the survey is explained and verbal permission to perform the survey in the village is obtained before any household (HH) is visited.

Informed consent from each selected HH head will be obtained at arrival and before the team enters the house for the interview, see Annex 5 'Household Consent Form'.

Data collection and analysis

Data will be collected by mobile devices, and if not possible by paper forms, by survey teams in the field (see annex 'Forms'). All data will be uploaded to a remoter server each evening, or whenever internet connection allows. Throughout the survey SCI will review the data collected at the end of each day to allow feedback to the team and make any adjustments to interviewer technique or the protocol.

Analysis of the data will include calculation of survey coverage and associated 95% confidence intervals using appropriate analytical tools that account for clustering in the data (i.e. interviewees clustered in HHs and villages, and IU if appropriate). Sub-group analysis (e.g. using multi-level logistic regression) will be used to test how coverage in SAC varies according to school attendance and gender, and in adults by gender. All analyses will be fully shared with collaborating partners in country.

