If people in the selected home refuse to participate, try to encourage participation. If they still refuse, indicate this on the survey form, and count this HH as one of the HHs visited, indicate this on the survey form. **DO NOT replace the house with another HH**.

If no-one is at home in the selected HH, return later in the day. If, again, nobody is at home, indicate this on the survey form in the "Household questions" section, and count this HH as one of the HHs visited. **DO NOT** replace the HH with another one⁵.

If there are no eligible individuals for interview in the HH (e.g. no SAC live at the address, or all HH members moved in after the drug distribution), note this on the survey form, do not ask the questions, **but replace the HH with the next HH in the direction of travel with any eligible interviewee.**

Selecting individuals within a household

- If the head of the HH agrees to participate, proceed with the interview.
- Two adults and all school-aged children (SAC) within each HH will be randomly selected for interview.
- SAC is all children aged 5 -14 years
- Adults is all people aged 15 or over

The steps to take for interviewing SAC within a HH are:

- 1. Write the name of each SAC (i.e. all children aged 5 -14) in the HH on a separate piece of paper. Include all SAC living in the HH, even if they are not in the HH at the time.
- 2. Begin interviewing the children who are available for interview

⁵ If this happens for many households (e.g. frequently >2 households/village) in several villages, the supervisors should discuss with the study co-ordinator to consider increasing the number of households to randomly select per village.

3. If a selected individual cannot be interviewed, record who they are and please see below.

The steps to take for interviewing adults within a HH are:

- Write the name of each adult (i.e. all individuals 15 or over) in the HH on a separate piece of paper.
 Include all adults living in the HH, even if they are not in the HH at the time.
- 2. Fold up the pieces of paper and put into a container
- 3. Pick out two pieces of paper
- 4. Interview the adults whose names are on the paper
- 5. If a selected individual cannot be interviewed, please see below

What to do if an individual cannot be interviewed

- If an individual (SAC or adult) cannot be interviewed then return later to try to interview them.

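### SO 2 compares reported coverage per registered person with survey coverage per person interviewed, counting missing answers as untreated, so a gap cannot be read as over-reporting

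*Protocol*

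**What the plan says.** **Objective.** Under Study Objectives, SO 2 is "To compare reported and validated coverage of PZQ and ALB for SAC and adults". The introduction says that such comparisons serve to detect over- and under-reporting in routine data.

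**Reported side.** The Background to the Coverage Survey describes routine coverage as treatments distributed with "population figures (often obtained from routine census figures) as the denominator". The tables under Reported coverage from the MDA instead place treated counts beside "REGISTRATION SCHOOL" and "REGISTRATION COMMUNITY" counts. They give one coverage percentage per platform and drug, with ages 5-14 and 15+ together.

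**Survey side.** Validated coverage is printed as "Total number of interviewed individuals that ingested the target drug Total number of interviewed individuals * 100" per cent. The note below it says that "people interviewed but with missing information on whether they ingested the drug will be assumed to have" not taken it. The rule is not limited to SO 1.

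**Who was offered treatment and who is interviewed.** Details of the MDA in Malawi 2017 describes school treatment plus "community-based treatments for children who do not attend school and adults in the high-risk areas". The survey draws its villages from a list of all villages in the district. Appendix B says "Two adults and all school-aged children (SAC) within each HH will be randomly selected for interview", and every resident aged 15 or over goes into the adult draw. Appendix D, under Sampling of individuals within a HH, limits adults to those eligible for treatment. Neither the validated-coverage formula nor the Appendix B steps carry that limit.

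**The concern.** SO 2 judges whether district tallies are accurate, so both percentages must refer to the same people. As written, a resident who was never registered can enter the survey denominator but not the reported one. An adult in a village where adults were not offered treatment is the plainest case. A missing answer also lowers the survey figure and leaves the reported figure unchanged. That is a cautious choice when coverage is set against the 75% target (SO 1). In SO 2 it pulls the survey figure down relative to the reported one. A district with accurate tallies could then be labelled as over-reporting and corrected for a fault it does not have.

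**Working it through.** **1. What the printed coverage is.** Treated total divided by registered total, for PZQ:

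| District | School (%) | Printed | Community (%) | Printed |
|---|---|---|---|---|
| Karonga | 98,580/116,003 = 85.0 | 85 | 36,888/41,952 = 87.9 | 88 |
| Rumphi | 55,118/63,016 = 87.47 | 87 | 28,681/32,430 = 88.4 | 88 |
| Dedza | 204,804/217,704 = 94.1 | 94 | 143,820/170,638 = 84.3 | 84 |
| Salima | 102,881/118,410 = 86.9 | 87 | 103,757/122,366 = 84.8 | 85 |
| Mchinji | 135,519/157,984 = 85.8 | 86 | 33,696/37,728 = 89.3 | 89 |
| Ntcheu | 134,369/166,428 = 80.7 | 81 | 75,539/88,307 = 85.5 | 86 |

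The ALB columns for these districts reproduce in the same way. The reported denominator is registration, not population.

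**2. The SO 2 groups.** SO 2 asks for SAC and adults. No printed percentage is for either group, but the age cells allow both to be computed across platforms.

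- Dedza SAC, PZQ: (81,557 + 91,239 + 35,080 + 38,567) / (86,956 + 95,754 + 44,496 + 45,678) = 246,443/272,884 = 90.3%. The printed values are 94 and 84.
- Dedza SAC, ALB: (55,483 + 61,791 + 20,586 + 23,626) / 272,884 = 161,486/272,884 = 59.2%. The printed values are 62 and 43.
- Rumphi community ALB, printed 58: SAC (2,562 + 2,447)/(2,967 + 2,928) = 85.0%, adults (6,809 + 6,990)/(12,950 + 13,585) = 52.0%. Setting survey SAC coverage against the printed 58 would be wrong by 27 points.

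**3. Adults.** Registered adults per registered SAC range from 35,329/160,383 = 0.22 in Mchinji to 101,978/138,798 = 0.73 in Salima. This fits selective registration of adults, as the MDA description implies, though it does not prove it. The survey applies no such selection of villages or adults.

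**4. Size, under assumptions.** Let u be the share of interviewed people who were neither registered nor treated, and m the share with a missing ingestion answer, unrelated to treatment. With accurate tallies, and residents otherwise matching the registers,

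validated = reported × (1 − u) × (1 − m).

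The protocol gives neither u nor m. Starting from 85%:

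| Assumption | Validated (%) | Gap (points) |
|---|---|---|
| m = 2 / 5 / 10%, u = 0 | 83.3 / 80.8 / 76.5 | 1.7 / 4.2 / 8.5 |
| u = 5 / 10 / 20%, m = 0 | 80.8 / 76.5 / 68.0 | 4.2 / 8.5 / 17.0 |
| u = m = 5% | 76.7 | 8.3 |
| u = m = 10% | 68.9 | 16.1 |

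**5. Yardstick.** The inputs in Appendix D reproduce the design: 1.96² × 0.25/0.09² = 118.6; design effect 1 + 23 × 0.1 = 3.3; 118.6 × 3.3 = 391. At 85% coverage the expected half-width is 1.96 × √(0.85 × 0.15 × 3.3/391) = 6.4 points. A 5% loss from one source stays inside it. A 10% loss from one source, or 5% from both, exceeds it.

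**The case against.** The strongest reply is that SO 2 does not commit to the printed coverage column. The tables are background, the Background section defines reported coverage over population, and a statistical analysis plan may align the two. The age and sex cells for the six districts with stratum data already allow a proper SAC figure. This stands in part: the denominator of the reported side is left unreconciled rather than fixed wrongly. It does not reach the survey side, where the protocol itself fixes both the formula and the missing-data rule.

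A reader might go further and infer that apparent over-reporting is built into the design. The documents do not support that. Absent and refusing people leave the survey denominator, which could raise validated coverage if they were treated less often. Treated but unregistered residents enter the survey numerator. In 2016 four of six districts showed no significant difference, and the other two split one higher and one lower, although the denominators used then are not given.

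A reader might also infer from the country community row that registration is unsound: 600,837 girls treated with PZQ against 583,686 registered is 102.9%, and the registration strata sum to 3,253,752 against a printed 3,467,590. But each district is analysed separately. In the six districts with stratum data the strata sum exactly and no treated cell exceeds its registered cell. The country row may simply have incomplete stratum entries.

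**Conclusion.** The point holds as a problem of interpretation: under the stated rules a gap between reported and validated coverage cannot be read as over-reporting. The missing-data part has a certain direction, since the rule can only lower the survey figure. The denominator part is firmest for adults, where the described target and the sampled population differ. For SAC the documents do not show that registers fall short of residents, so neither the size nor the direction of any denominator effect is established. The illustrative gaps of 1.7 to 17.0 points for a single source rest wholly on the assumed values of u and m, on unregistered people being untreated, and on missingness unrelated to treatment.

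**What to change.** For SO 2:

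1. Compute reported coverage per district separately for ages 5-14 and 15+, summing the school and community cells. State the denominator, so that the Background and the tables agree. Give a population-based figure as a sensitivity analysis where one is available. It should not replace the registration figure as primary, because projections carry their own error and would not cure the adult mismatch.
2. Restrict the adult comparison to surveyed villages where treatment included adults, which question 14 of the village form already records. Reconcile the MDA description, the validated-coverage formula, the village and adult selection steps, and the eligibility wording in Appendix D. The 15+ cells also contain people registered at school (in Dedza 17,981 + 17,013 = 34,994 of 115,458, or 30%), so show the community-only adult figure beside the combined one.
3. Keep missing as not taken for SO 1. For SO 2, use the estimate excluding missing answers, with the all-untreated value as a bound, and report the number missing.

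The cost is one or two table columns, no new fieldwork, and less precision for adults. If, as an assumption, half the villages qualified, the 6.4-point half-width would become 6.4 × √2 ≈ 9.1 points.
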